Edema	 Normal, no swelling  Slight, beyond normal and regional  Mild, mild conjunctival swelling, beyond normal, regional  Moderate, conjunctival swelling moderately  Severe, large conjunctival swelling
Subconjunctival hemorrhage	 Nil, no bleeding  Slight, flat and less than 1 quadrant  Mild, bulging, and 1 quadrant, or flat and more than 1 quadrants

	 Moderate, bulging and >1 quadrant, but less than 2 quadrants  Severe, bulging and more than 2 quadrants
Other conjunctival lesions	 No  Yes, Please describe: _____
2. Cornea (study eye)	
Edema	 Nil, transparent and clear  Slight, micro and local epithelial haze  Mild, turbid vitreous appearance and may contain tiny droplets  Moderate, turbid vitreous appearance with a large number of vacuoles  Severe, bullous and / or stromal edema, localized or diffuse, with or without matrix streaks
Other corneal lesions	 No  Yes, Please describe: _____

Slit Lamp Examination Form (study eye)-II

3. Anterior chamber (study eye)	
Cell number	 Nil, no cells  Slight, 1-5 cells  Mild, 6-25 cells  Moderate, 26-50 cells  Severe, the number of cells is too large to count
Anterior chamber flare	 Nil, no Tyndall effect  Slight, almost cannot distinguish the Tyndall effect  Mild, slight brightness  Moderate, strong brightness  Severe, very strong and aqueous humor is white or milky
Other lesions	 No  Yes, Please describe: _____

4. Iris / pupil (study eye)	
Iris / pupil (study eye)	Clinically significant abnormality:  No  Yes, Please describe: _____
5. Lens (studyeye)	
Lens (study eye)	 Complete  Artificial  Nil
Other lesions	 No  Yes, Please describe: _____
Transparency	
Cortex	 Nil  There are turbidity, but below standard pictures   There are turbidity, and the severity of the standard picture is the same or more serious   Not applicable
Nucleus	 Nil  Turbid, but below standard pictures   Turbid, the same or more serious than standard pictures   Not applicable
Posterior capsule	 Nil  Turbid, but below standard pictures   Turbid, the same or more serious than standard pictures   Not applicable

Slit Lamp Examination (study eye)-II

6. Vitreum (study eye)	
Anterior vitreous cell count	 Nil, no cells  Slight, 1-10 cells  Mild, 11-30 cells  Moderate, 30-50 cells  Severe, >50 cells
Other lesions	 No  Yes, Please describe: _____
Vitreous / anterior retinal hemorrhage	 Nil  Slight  Mild  Moderate  Severe
Air volume in vitreous cavity	 Nil  $\leq 30\%$  $>30\%$, and $\leq 50\%$  $>50\%$, and $\leq 70\%$  $>70\%$  Not applicable
Silicone oil volume in vitreous cavity	 Nil  $>50\%$, and $\leq 70\%$  $>70\%$, and $\leq 90\%$  $>90\%$  Not applicable
7. Macular and retina (research eye)	
Macular hole	 Nil  Hole diameter $\leq 1/3$ PD  Hole diameter $>1/3$ PD, and $\leq 1/2$ PD  Hole diameter $>1/2$ PD, and ≤ 1 PD

	 Hole diameter > 1PD
Retinal detachment	 Nil  Yes, Please describe:  Within the arcade  beyond the arcade, and within the equator  Beyond the equator
Peripheral retinal split holes	 No  Yes, Please describe: _____
Posterior scleral staphyloma	 No  Yes, Please describe: _____
Other lesions	 No  Yes, Please describe with words or pictures: _____

Attachment 3

Low vision quality of life questionnaire

5=Nil; 4-2=Moderate; 1=Severe; x=Unable to do.

How well do you know about your current vision? 5=Much, 1=Little

1. Because of your vision, in the following circumstances, do you feel difficult?.	
1. Feel tired (for example, only after a short time using eyes)	 5  4  3  2  1  x  Others
2. At home at night	 5  4  3  2  1  x  Others
3. Look at things in the right amount of light	 5  4  3  2  1  x  Others
4. Feel the light glare (such as car lamp or sun make you dazzle)	 5  4  3  2  1  x  Others
5. Look at road signs	 5  4  3  2  1  x  Others
6. Watch TV (or enjoy pictures)	 5  4  3  2  1  x  Others
7. Look at moving objects (such as cars on the road)	 5  4  3  2  1  x  Others
8. Determine the distance or depth of objects	 5  4  3  2  1  x  Others
9. See the stairs or railings	 5  4  3  2  1  x  Others
10. Walk outdoors (e.g., on an uneven sidewalk)	 5  4  3  2  1  x  Others
11. Cross the street when there is vehicles	 5  4  3  2  1  x  Others
12. Generally speaking	 5  4  3  2  1  x  Others
2. Because of your vision, so you	
1. Not satisfied with your current life	 5  4  3  2  1  x  Others
2. Be upset about not being able to do some work	 5  4  3  2  1  x  Others
3. Visiting relatives and friends is limited	 5  4  3  2  1  x  Others
4..How well do you know about your current vision	 5  4  3  2  1  x  Others
3. If you use visual aids or glasses, if there are difficulties when doing the following things	
1. Identify uppercase fonts	 5  4  3  2  1  x  Others
2. Read newspaper articles and books	 5  4  3  2  1  x  Others
3. Read labels (for example, on a bottle or kit)	 5  4  3  2  1  x  Others
4. Reading letters	 5  4  3  2  1  x  Others

5. Use some tools (such as sutures or scissors)	 5  4  3  2  1  x  Others
4. If you use visual aids or glasses, if there are difficulties when doing the following things	
1. Watch the clock to know the time	 5  4  3  2  1  x  Others
2. Sign or write cards	 5  4  3  2  1  x  Others
3. Identify your own handwriting	 5  4  3  2  1  x  Others
4. Do daily activities (such as housework)	 5  4  3  2  1  x  Others

Attachment 4

Abbreviations

Abbreviations and special terms	Explanation
ALT	Alanine aminotransferase
AST	Aspartate aminotransferase
BCVA	Best corrected visual acuity
CREA	Serum creatinine
Wide angle CP	Wide angle fundus color photography
GGT	Glutamyl transferase
HCV	Hepatitis C virus
HIV	Human immunodeficiency virus
LDH	Lactate dehydrogenase
LogMAR visual acuity	Standard logarithmic visual acuity
MHRD	Macular hole complicated with retinal detachment
INR	International normalized ratio
IOP	Intraocular pressure
OCT	Optical coherence tomography

OD	Right eye
OS	Left eye
OU	Both eyes
PDR	Proliferative diabetic retinopathy
PVR	Proliferative vitreoretinopathy
TB	Total bilirubin
TPPA+RPR	Treponema pallidum antibody gelatin particle agglutination test + syphilis serum test
VA	Vision acuity

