- 9) With other causes which may result in macular hole associated-retinal detachment at screening or baseline, except high myopia;
- 10) Previously underwent scleral buckling surgery;
- 11) With current or planned medication known to have toxic effects on the lens, retina or optic nerve, including hydroxychloroquine, chloroquine, hydroxychloroquine, tamoxifen, phenothiazine and ethambutol;
- 12) With laboratory abnormalities, such as ALT, AST, TB, GGT, LDH, exceeded the normal limit by more than 2 times, and CREA or blood urea nitrogen exceeded 1.2 times the normal limit;
- 13) With abnormal coagulation function (defined as more than normal prothrombin time for 3 seconds or more, more than 1.5 of the international standard ratio (INR), activated partial thromboplastin time of 10 seconds or longer than the upper limit of normal time);
- 14) Patients who participated in any clinical study of medication within 3 months prior to screening (excluding vitamins and minerals)

6. Exit criteria

Exit criteria

- 1) Due to adverse events, especially severe adverse events, the researchers consider withdrawal of patients based on concerns of safety and ethics;
- 2) Drop out;
- 3) The patients voluntarily withdraw the informed consent;
- 4) Serious violation of the study protocol due to the subjects or investigators' reasons;
- 5) Other reasons that the researchers believe for quitting the study

7. Treatment

Group 1: The patients in Group 1 are treated by the surgical method of standard 3-port 23 gauge pars plana vitrectomy + internal limiting membrane peeling + air-fluid exchange + silicone oil infusion

Group 2: The patients in Group 2 are treated by the surgical method of standard 3-port 23 gauge pars plana vitrectomy + internal limiting membrane peeling + inverted internal limiting membrane insertion + air-fluid exchange.

8. Inspection and observation schedule

Period Project	Screening period	Randomization period	Follow up period ¹								
	Baseline	Treatment	V1	V2	V3	V4	V5	V6	V7	Termination	Unscheduled visit
Visiting time	-7~0d	0d	1d	1w	2w	4w	8w	12w	6m	12m	—
Informed consent	×										
Inclusion and exclusion criteria	×	× ²									

Demographic data	×											
Chief complaint and current medical history	×											
Medical history	×											
Previous surgery/trauma history and ocular surgery history	×											
Diagnosis	×											
Vital signs ³	×		×	×	×	×	×	×	×	×	×	×
General physical examination	×		×	×	×	×	×	×	×	×	×	×

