Slit lamp examination ⁴ (binocular)	×											

Slit lamp examination ⁵ (study eye)				×	×	×	×	×	×	×	×	×
ECG and chest radiography ⁶	×											
Laboratory examination ⁷	×											
Auxiliary examination ⁸	×			×	×	×	×	×	×	×	×	×
Low vision quality of life questionnaire ⁹	×							×	×	×	×	
History change		×										
Randomization		×										
Surgical treatment		×										

Subject files	×											
Adverse events ¹⁰		×	×	×	×	×	×	×	×	×	×	×
Previous / combined medication ¹¹	×	×	×	×	×	×	×	×	×	×	×	×
Quit in advance			×	×	×	×	×	×	×	×		
Statistical summary of major endpoints									×			
Summary of the study										×		
Unscheduled visits												×
Research statistics summary										×		

Remarks

(1) Visit Window: Visit 2 to visit 6; each visit has a window period of ± 3 days; visit 7 and end visit allow a window period of ± 7 days.

(2) If both the eyes meet the requirements in the screening, the eye with the poorer BCVA should be selected as the study eye, unless for medical reasons, the researchers believe that the other eye is more suitable for the research. The study eye will undergo surgical treatment according to the protocol. If the BCVA damage of the contralateral eye is caused by macular hole associated with retinal detachment secondary to high myopia, according to the

judgment of the researchers, the contralateral eye can also be recommended for surgical treatment. The contralateral eye was labeled as the contralateral eye for treatment. The treatment of bilateral eyes should not be performed on the same day.

(3) Vital signs, including blood pressure, pulse, respiration, armpit temperature, should be measured after sitting for 5 minutes.

(4) Slit lamp examination: Use “Slit Lamp Examination Form-I” (Attachment 1). Accept the examination results carried out before the informed consent signature during the same hospitalization.

(5) Slit lamp examination: Use “Slit Lamp Examination Form-II” (Attachment 2).

(6) ECG, chest radiography: Accept the examination results carried out before the informed consent signature during the same hospitalization.

(7) Laboratory examination includes routine blood test, blood biochemistry, routine blood coagulation, hepatitis B quantification, HCV antibody, TPPA+RPR and HIV antibody. Accept the examination results carried out before the informed consent signature during the same hospitalization.

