Reattachment rate of retinal detachment: Use fundus examination combined with B-scan ultrasound, optical coherence tomography (OCT) to observe the reattachment rate of retinal detachment within 12 months after the surgery.(The reattachment rate assessment is performed 12 months after the first surgery among the patients with air tamponade. The reattachment rate assessment is performed 12 months after the first surgery among the patients with silicone oil tamponade, and the silicone oil removal is performed 6 months after the previous surgery.)

Postoperative complication rate

10. Adverse event

(1) Adverse events (AE) refer to any adverse event that occurs during clinical studies, but do not necessarily have causal relationship with the surgery.

Safety evaluation should be carried out from the signature of the informed consent until the end of the study, according to management requirements (Adverse events or serious adverse events should be reported).

(2) Severe adverse events (SAE) refer to the occurrence of hospitalization, prolonged

hospitalization, disability, incapacity, life-threatening or death, congenital malformations during the clinical trials.

(3) Record of adverse events

During the study, all adverse events should be recorded. Records should include the name of AE (using the standard medical terminology), the date of AE occurrence and disappearance / stabilization, severity, impact on the surgery, relationship with the surgery, treatment measures and outcomes.

(4) Reports of serious adverse events

If serious adverse events occur, researchers must fill in the report of serious adverse events. The report should be signed and dated, and be reported to the ethics committee within 24 hours.

11. Target case load and sample size calculation

Target case load: 38

The study uses the superiority design. According to the references and the professional judgment, macular hole closure rate is 25% in the control group (group 1), while in the experimental group (group 2), macular hole closure rate is 65%. The significant level α is 0.05, and test performance (1- beta) is 0.80. The software of NCSS PASS 14 is used, and each group has 17 cases with the loss rate of 10%. The final sample size is 38.

12. Randomization

Stratified randomization is conducted according to the extent of retinal detachment [type 1 (within the arcade area), type 2 (beyond the arcade area)]. The software of NCSS PASS 14 will be used. The study includes 2 groups.

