This study uses a new surgical method (intraocular sterilized air tamponade) to assess its effect on the prognosis of macular hole retinal detachment secondary to high myopia.

This study compares this new type of surgery with the current commonly used surgery (vitrectomy combined with internal limiting membrane peeling + silicone oil infusion) on the prognosis of macular hole retinal detachment secondary to high myopia.

Study protocol

Title:

A Single Center, Randomized and Controlled Clinical Study of Inverted Internal Limiting Membrane Insertion Combined with Air Tamponade in the Treatment of Macular Hole Retinal Detachment in High Myopia

Key word:

Surgical procedures, air tamponade, high myopia, macular hole retinal detachment

Study design:

Single center, randomized, controlled, interventional, prospective

Aim:

The aim of this study is to evaluate the effectiveness and safety of different surgical procedures for patients with macular hole retinal detachment secondary to high myopia.

Primary Outcome Measure:

To evaluate the effectiveness of different surgical procedures by evaluating the following indicators:

Macular hole closure rate: Fundus examination combined with optical coherence tomography (OCT) are performed 3 months after surgery.

Secondary Outcome Measure:

To evaluate the effectiveness and safety of different surgical procedures by evaluating the following indicators:

Best corrected visual acuity (LogMAR): 6 months after the surgery

Reattachment rate of retinal detachment: Use fundus examination combined with B-scan ultrasound, optical coherence tomography (OCT) to observe the reattachment rate of retinal detachment within 12 months after the operation. (The reattachment rate assessment is performed 12 months after the first surgery among the patients with air tamponade. The reattachment rate assessment is performed 12 months after the first surgery among the patients with silicone oil tamponade, and the silicone oil removal is performed 6 months after the previous surgery.)

Postoperative complication rate of ocular adverse events

Postoperative complication rate of the non ocular adverse events

Postoperative complication rate of severe adverse events

Key inclusion criteria

Prior written consent is required before any assessment.

Study eye selection criteria:

Age: ≥ 18 years old, ≤ 75 years old

Visual impairment is caused by macular hole associated with retinal detachment secondary to high myopia

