The change of the extent of foveal ellipsoid zone damage from baseline to the 12th month after the surgery relative to baseline, and the difference between each group

The change of the external limiting membrane integrity of fovea from baseline to the 12th month after the surgery relative to baseline, and the difference between each group

Describe the number of retreatment and retreatment modalities for patients with different surgical procedures over a period of 12 months

Evaluate the safety of different surgical procedures by assessing the type, frequency and severity of ocular adverse events and non-ocular adverse events or severe adverse events during 12 months

Data analysis

(1) Validity analysis: Descriptive statistical method is used to describe the research indicators. Univariate analysis of continuous variables is performed using ANOVA, and univariate analysis of categorical variables is performed using chi square test. The repeated measurement data are analyzed by mixed effect model. The population of effectiveness analysis is the population of people with intention to be treated.

(2) Safety analysis: The safety assessment of clinical parameters (including adverse events, laboratory tests, vital signs, etc.) will be carried out. Descriptive statistics method is adopted. The safety analysis of the population is the population of all groups received treatment.

(3) Subgroup analysis: To determine whether the therapeutic effects of different subgroups are consistent, the component outcomes (and 95% confidence interval (CI)) are estimated for the major endpoints within the subgroup of the following categorical variables:

The type of retinal detachment [type 1 (within the arcade area), type 2 (beyond the arcade area)]

Gender (male and female)

CRC assistance

The study requires one to two clinical research coordinator (CRC)

Responsibilities:

-
- (1) Contact the subjects before 3-7 days before a follow-up;
 - (2) Communicate with the director in advance, and make appointments for patient follow-ups;
 - (3) Arrange the relevant examination for the patients;
 - (4) Have good communication skills;
 - (5) Fill in Case Report Form.

Benefit status of subjects

The therapy in this study may help to further control the patient's condition, to optimize the treatment of the disease, to provide the necessary advice for the future treatment of patients, to provide useful information for treatment or disease;

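### All visits are counted from the first surgery, so Group 1's planned oil removal at 6 months has almost no scheduled follow-up before month 12 and the 12-month complication comparison rests on unequal examination per operation

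*Protocol*

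**What the plan says.** The schedule in Summary section 8 has a single time row for both arms: "Visiting time -7~0d 0d 1d 1w 2w 4w 8w 12w 6m 12m". Surgical treatment is marked once, in the day-0 column. Remark (1) sets the windows: "Visit 2 to visit 6; each visit has a window period of ± 3 days; visit 7 and end visit allow a window period of ± 7" (in days).

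Oil removal is not in the Group 1 treatment description (Summary section 7, and again under Study design) or in the schedule. It appears only in the parenthesis explaining the reattachment outcome (Summary section 9, repeated under Secondary Outcome Measure): "the silicone oil removal is performed 6 months after the previous surgery". The same parenthesis ties the late assessment to the first operation: "The reattachment rate assessment is performed 12 months after the first surgery among the patients with silicone oil tamponade". No window is given for the removal, nor its order relative to V7, nor any visit that follows it.

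On safety, Secondary Outcome Measure lists "Postoperative complication rate of ocular adverse events", with companion rates for non-ocular and severe events. Outcome evaluation calls for "assessing the type, frequency and severity of ocular adverse events and non-ocular adverse events or severe adverse events during 12 months".

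Two provisions bear on how events are found. Remark (10) has adverse events collected from consent to study end. Remark (8)(e) gives unscheduled visits the same auxiliary examinations as the later scheduled visits.

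**The concern.** Calendar time since randomised surgery is covered identically in the two arms. Time since an operation is not. Both arms are examined closely after the first surgery, but only Group 1 is due a second intraocular operation, and it falls at the start of the longest gap in the calendar.

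Some complications show themselves only on examination: a pressure change, mild inflammation, a small haemorrhage. If such an event follows oil removal and settles before month 12, no scheduled visit would find it. The same event after the first surgery would meet several scheduled visits. The 12-month complication comparison then mixes a closely examined period with a sparsely examined one, and the sparse one contains an operation that only the control strategy includes. At stake is how the safety of the two strategies compares, which is part of the stated aim.

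**Working it through.** The protocol gives no complication rate and no detection rate, so there is no figure of its own to reproduce on this point. The check is a visit count, followed by an illustration on assumed rates.

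**Inputs.** Visit times come from the schedule in Summary section 8. Oil removal at 6 months comes from Summary section 9. The windows come from Remark (1): "visit 7 and end visit allow a window period of ± 7 days". One month is taken as 365.25/12 = 30.44 days, so 6 months = 182.6 days.

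**Scheduled visits after each planned operation** (removal taken at exactly 6 months, V7 not later than removal):

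| Time after the operation | First surgery (both arms) | Oil removal (Group 1 only) |
|---|---|---|
| 1 week | 2 (1d, 1w) | 0 |
| 4 weeks | 4 (adds 2w, 4w) | 0 |
| 12 weeks | 6 (adds 8w, 12w) | 0 |
| 6 months | 7 (adds 6m) | 1 (the 12m visit) |

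**Length of the gap.** From the 6-month to the 12-month visit is nominally 182.6 days. With both windows it runs from 182.6 − 14 = 168.6 to 182.6 + 14 = 196.6 days, that is 169 to 197.

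**Exception.** Because the order is not fixed, a V7 held at the end of its window could fall up to 7 days after a removal done at exactly 6 months. That would be one early examination, and it would come by chance.

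**Illustration on assumed rates (none are in the documents).** Let r1 be the complication risk of the first surgery in either arm, r2 the risk of oil removal, and d the share of removal complications that get recorded. Assume first-surgery complications are fully recorded and the two risks are independent. Then

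recorded Group 1 rate = 1 − (1 − r1)(1 − r2·d), and Group 2 rate = r1.

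With r1 = 20%:

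| r2 | d = 1 (true rate) | d = 0.5 | d = 0 |
|---|---|---|---|
| 10% | 1 − 0.8×0.90 = 28% | 1 − 0.8×0.95 = 24% | 20% |
| 20% | 1 − 0.8×0.80 = 36% | 1 − 0.8×0.90 = 28% | 20% |
| 30% | 1 − 0.8×0.70 = 44% | 1 − 0.8×0.85 = 32% | 20% |

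The under-count in Group 1 is therefore 0 points if everything is captured, 4 to 12 points if half is, and 8 to 24 points if nothing is. With 38/2 = 19 patients per arm, the extremes are 0 and 0.24 × 19 = 4.6 patients. The result is driven almost wholly by d, which the documents do not supply.

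**The case against.** A reader might infer that the 12-month comparison does under-count the control arm and makes it look safer than it is. The documents do not support that as a fact, for five reasons.

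- Summary section 10 requires every adverse event to be recorded with its dates and its relation to surgery. Unscheduled visits carry slit lamp, pressure, OCT, fundus photograph and B-scan. Symptomatic events can be caught this way.
- A redetachment that persists would be seen at the 12-month assessment, and one that is operated on enters the 12-month retreatment outcome. The exposure is limited to silent or transient findings.
- The definition of a serious event includes hospitalisation with no exception for a planned admission. Read literally, an admission for oil removal could add to Group 1's count, which pushes the other way.
- Group 2 eyes may also be retreated, and retreatment does not restart their calendar either. It is too strong to say that every Group 2 operation is followed closely.
- Anchoring both arms at the first surgery is a legitimate choice, and the safety analysis is descriptive.

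All of this stands, and it removes any claim to a known size or direction. It does not remove the inequality. Nothing requires an unscheduled visit after removal, and whether one occurs depends on patients and surgeons who are not masked. The coordinator's contact duty is tied to upcoming follow-ups, so no planned contact falls early after removal. Tabulating by period can be left to a statistical analysis plan, but no such plan can recover findings that nobody examined for.

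**Conclusion.** The point holds as one of unequal and unspecified ascertainment. Scheduled visits in the 12 weeks after an operation number six after the first surgery and none after oil removal, apart from a V7 that happens to fall late. The next scheduled examination after the 6-month visit comes 169 to 197 days later. The 12-month complication comparison may therefore miss silent or transient Group 1 events after removal.

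How many it misses, and which way the net bias runs, cannot be fixed. The 0 to 24 points in the illustration rest on assumed risks and an assumed capture share, and with full capture the shortfall is zero. The visit count rests only on the printed calendar and on removal at 6 months.

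The 3-month primary outcome and N = 38 are untouched. This is an inexpensive improvement to the safety comparison, not a flaw in the main result.

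**What to change.** 1. Reconcile the schedule and treatment description with the oil-removal text, including the order of removal relative to V7. Which order and what timing are for the investigators to settle.
2. Have the existing unscheduled-visit page (slit lamp Form II, pressure, OCT, fundus photograph) completed at clinic visits that take place after removal, so that what is seen there reaches the trial data.
3. Keep the 12-month complication comparison as the comparison of strategies. Replacing it with day 0 to V7 would drop the real burden of the second operation.
4. Beside it, add a table split into day 0 to V7 before removal, and the period after. If V7 precedes removal, both arms have the same seven scheduled visits in the first part. Attribute each event to an operation, and note under the later part that scheduled examination per operation is unequal.
5. Count the planned admission for oil removal separately from serious adverse events.

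The cost is a protocol clarification, slightly more recording on a form that already exists, and one extra table. The split helps only as far as post-removal visits occur and are recorded.

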13. Masking method

In this study, the third party independent evaluation method is used to evaluate the results of the study. The analyzer is in the masking state, and the patients and the surgeons are in the non-masking state.

14. Statistical data processing

(1) Validity analysis: Descriptive statistical method is used to describe the research indicators. Univariate analysis of continuous variables is performed using ANOVA, and univariate analysis of categorical variables is performed using chi square test. The repeated measurement data are

analyzed by mixed effect model. The population of effectiveness analysis is the population of people with intention to be treated.

(2) Safety analysis: The safety assessment of clinical parameters (including adverse events, laboratory tests, vital signs, etc.) will be carried out. Descriptive statistics method is adopted. The safety analysis of the population is the population of all groups received treatment.

(3) Subgroup analysis: To determine whether the therapeutic effects of different subgroups are consistent, the component outcomes (and 95% confidence interval (CI)) are estimated for the major endpoints within the subgroup of the following categorical variables:

The type of retinal detachment [type 1 (within the arcade area), type 2 (beyond the arcade area)]
Gender (male and female)

15. Study implementation period (Anticipated)

April 7th, 2017 to April 6th, 2020

16. Quality Control

The researcher and laboratory personnel involved in this project must have the professional knowledge and experience required in the study protocol;

The researchers and other staff involved in the study perform their duties, and strictly follow the clinical trial plan and adopt standard operating procedures to ensure the implementation of the quality control and quality assurance system;

To ensure that the data is complete, accurate, authentic and reliable, all the relevant observation results and findings need to be verified in each phase of the clinical trials;

The researchers and other staff who participated in the study have sufficient time and reliable sources of subjects for the study;

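### The stated 80% power with 17 per group holds only at an unstated one-sided 5% level; the two-sided chi-square test gives about 69% (73% with 19 per group)

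*Protocol*

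**What the plan says.** The sample-size paragraph appears twice with the same content: in section 11 of the Summary and under Sample size calculation in the Specific Study Protocol. It assumes macular hole closure of 25% in group 1 and 65% in group 2, and continues: "The significant level α is 0.05, and test performance (1- beta) is 0.80". The result is "each group has 17 cases with the loss rate of 10" per cent, for a final total of 38.

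On direction, the paragraph says only "The study uses the superiority design". Neither copy uses the words one-sided or two-sided, and one-sided testing is mentioned nowhere else.

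The analysis is described in section 14 (1) and repeated under Data analysis (1). For categorical outcomes it states that "univariate analysis of categorical variables is performed using chi square test". It mentions no direction and no continuity correction. On the analysis set: "The population of effectiveness analysis is the population of people with intention to be treated".

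**The concern.** A sample size for two proportions depends on whether alpha is one- or two-sided. A chi-square statistic squares the difference between the groups, so a departure in either direction counts against the null hypothesis. Used at 0.05 in the usual way, it is a two-sided test. For 25% against 65%, 17 per group looks too few for 80% power on that basis.

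This is the protocol's only power figure. A reader faced with a non-significant closure result in a trial of 38 patients would use it to judge how much that result excludes. If the true power is nearer 70%, a null result is weaker evidence than the protocol implies.

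**Working it through.** **Inputs** (section 11; same in Sample size calculation): p1 = 0.25, p2 = 0.65, difference 0.40, alpha 0.05, power 0.80, 17 per group, 10% loss, total 38. Equal allocation is implied by a single figure per group. Then p1(1 − p1) = 0.1875, p2(1 − p2) = 0.2275, their sum is 0.415, and the pooled rate is 0.45, so 2 × 0.45 × 0.55 = 0.495.

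**Step 1. Loss inflation.** 17 / 0.9 = 18.9, so 19 per group and 38 in total. This reproduces.

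**Step 2. Where 17 comes from.** The two standard formulas per group are

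- unpooled: n = (z_α + z_β)² × 0.415 / 0.40²
- pooled: n = (z_α √0.495 + z_β √0.415)² / 0.40²

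with z_β = 0.842, and z_α = 1.645 (one-sided) or 1.960 (two-sided).

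| Alpha 0.05 | Unpooled | Pooled |
|---|---|---|
| One-sided | 16.04 → 17 | 18.05 → 19 |
| Two-sided | 20.36 → 21 | 23.07 → 24 |

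Exact enumeration sums the binomial probabilities of all outcome pairs that the test rejects. For the one-sided pooled z-test it gives 77.3% at 16 per group and 80.9% at 17, so 17 is the first size to reach 80%. Two routes therefore lead to 17, and both are one-sided. No two-sided method tried gives 17.

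**Step 3. Power of a two-sided 5% test at the planned size.**

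| Test | 17 per group | 19 per group |
|---|---|---|
| Uncorrected chi-square, exact | 69.5% | 72.9% |
| Pooled normal approximation | 66.3% | 71.4% |
| Unpooled z, exact | 69.8% | 77.7% |
| Unpooled formula | 72.6% | 77.2% |
| Yates-corrected chi-square, exact | 55.6% | 57.9% |
| Fisher's exact test | 55.6% | 63.1% |

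None reaches 80% at either size. For the uncorrected chi-square test the chance of missing the effect is 100 − 69.5 = 30.5% at 17 and 100 − 72.9 = 27.1% at 19, against the planned 20%. With Yates or Fisher at 17 it is 100 − 55.6 = 44.4%.

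**Step 4. What 80% would need.** Exact power of the two-sided uncorrected chi-square test is 78.1% at 22 per group and 81.1% at 23, so 23 is the first size at or above 80%. After 10% loss, 23 / 0.9 = 25.6, so 26 per group and 52 in total. The pooled formula's 24 gives 24 / 0.9 = 26.7, so 27 per group and 54 in total. Alternatively, with 17 per group and control closure at 25%, power reaches 80% only if experimental closure is about 70%.

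**The case against.** The strongest reply is that nothing has been miscalculated. The stated inputs do yield 17 on a one-sided basis, a superiority design with a better rate expected in the experimental group is compatible with a directional calculation, and the one-sided z-test is the signed root of the same chi-square statistic. The protocol says neither one-sided nor two-sided, so the two-sided reading is inferred too. That is fair, and the point should be put conditionally: the figure lacks its basis, and on the ordinary reading of the named test it is wrong. It still needs correcting, because a reader who applies a chi-square test at 0.05 gets about 69%, and a one-sided intention would have to be written down to be relied on.

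The one-sided reconstruction is also not unique: the pooled formula gives 19 rather than 17, and the procedure chosen in the software is not named. So 17 is consistent with a one-sided level but does not prove that one was used.

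Effectiveness is analysed by intention to treat, so 19 per group may be the fairer basis. Power is then 72.9%, still short of 80%. The Yates and Fisher figures concern tests the protocol does not name, and they serve only as a lower range.

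The shortfall itself concerns power and does not change the type I error of a given test. Confirming a one-sided 5% level would, however, mean accepting a nominal 5% false-positive risk in favour of the new surgery, against 2.5% in that direction under a two-sided test. In addition, the uncorrected chi-square test is only nominally a 5% test here: enumeration gives a maximum size of about 5.8% at both 17 and 19 per group.

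**Conclusion.** The concern holds. If the chi-square test is read as two-sided at 0.05, the stated 80% is about 69% at 17 evaluable per group and about 73% at 19, a shortfall of roughly 7 to 11 percentage points. The conclusion does not depend on the choice of formula: no two-sided variant tried exceeds 72.6% at 17 or 77.7% at 19. It assumes the protocol's own closure rates, equal allocation, and the ordinary undirected use of the only test named. That the calculation was one-sided is an inference from the number 17. The loss adjustment and the total of 38 follow correctly from 17.

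**What to change.** State the sidedness in both sample-size paragraphs and give the power that goes with it, keeping the total at 38. Suggested wording:

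> With 17 evaluable patients per group, a two-sided 5% uncorrected chi-square test has about 69% power (about 73% if all 19 per group are analysed) to detect closure of 25% versus 65%; 17 per group corresponds to 80% power only at a one-sided alpha of 0.05.

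If the sponsor did intend a one-sided 5% test, both sample-size paragraphs and both analysis sections should say so, so that the power and the test agree.

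The cost is the wording of two paragraphs (four on the one-sided route) and, on the two-sided reading, a less favourable stated power. It needs no extra patients and no change to the conduct of the trial. Keeping 80% power on a two-sided basis would instead require 52 to 54 patients.
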